The 3 dosing intervals are associated with 3 different dose-escalation decisions. The under-dosing interval corresponds to a dose escalation (E), over-dosing corresponds to a dose de-escalation (D), and proper-dosing corresponds to remaining at the current dose (R). Given a dosing interval and a probability distribution, the unit probability mass (UPM) of that dosing interval is defined as the probability of a patient belonging to that dosing interval divided by the length of the dosing interval. The mTPI design calculates the UPMs for the 3 dosing intervals, and the one with the largest UPM informs the corresponding dose-finding decision, which is the dose level to be used for future patients. For example, if the under-dosing interval has the largest UPM, the decision will be to escalate, and the next cohort of patients will be treated at the next higher dose level. Ji and collaborators have demonstrated that the decision based on UPM is optimal in that it minimizes a posterior expected loss (ie, minimizes the chance of making a wrong dosing decision).

The dose finding phase of the trial uses a modified version of the mTPI design that maximizes the number of evaluable patients treated at each dose level at 6. Dose finding is completed when 6 DLT-evaluable patients have been treated at the highest dose with a DLT rate  $< 0.33$ .

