#### **BOR Based on Confirmed Responses:**

- CR = at least two determinations of CR at least 4 weeks apart and before first documentation of PD
- PR = at least two determinations of PR or better (PR followed by PR or PR followed by CR) at least 4 weeks apart and before first documentation of PD (and not qualifying for a CR)
- SD (applicable only to patients with measurable disease at baseline) = at least one SD assessment (or better)  $\geq$  6 weeks after the 'start date' and before first documentation of PD (and not qualifying for CR or PR).
- Non-CR/non-PD (applicable only to patients with non-measurable disease at baseline) = at least one non-CR/non-PD assessment (or better)  $\geq$  6 weeks after the 'start date' and before first documentation of PD (and not qualifying for CR or PR).
- PD = first documentation of PD  $\leq$  12 weeks after the 'start date' (and not qualifying for CR, PR, SD or non-CR/non-PD).
- NE: all other cases.

An objective status of PR or SD cannot follow one of CR. SD can follow PR only in the rare case that tumor increases by less than 20% from the nadir, but enough that a previously

documented 30% decrease from baseline no longer holds. If this occurs, the sequence PR-SD-PR is considered a confirmed PR. A sequence of PR – SD – SD – PD would be a best response of SD if the window for SD definition has been met.

**Objective Response (OR)** is defined as confirmed BOR of CR or PR according to RECIST v1.1.

Patients who do not have a post-baseline radiographic tumor assessment due to early progression, who receive anti-cancer therapies other than the study treatments prior to reaching a CR or PR, or who die, progress, or drop out for any reason prior to reaching a CR or PR will be counted as non-responders in the assessment of OR. Each patient will have an objective response status (0: no OR; 1: OR). OR rate (ORR) is the proportion of patients with OR in the analysis set.

ORR by treatment group will also be calculated along with the 2-sided 95% CI using the Clopper-Pearson method (exact CI for a binomial proportion as computed by default by the FREQ procedure using the EXACT option).

In addition, the frequency (number and percentage) of patients with BOR of CR, PR, SD, non-CR/non-PD (applicable only to patients with non-measurable disease at baseline), PD, and NE will be tabulated. Patients with BOR of NE will be summarized by reason for having NE status. The following reasons will be used:

- No baseline assessment

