### **6.2.5. Biomarker endpoints**

Biomarkers will be summarized at all appropriate timepoints. For soluble proteins this is screening, Lead-in PK D1, C1D1, C2D1, C3D1, C4D1, C6D1, EOT and follow-up at day 30. For Anti-avelumab Antibodies, this is C1D1, C2D1, C3D1, C4D1, C6D1, C8D1, then Q12W, and 30 days after end of avelumab treatment. For biomarkers from Archival FFPE Tumor Tissue Block, this is screening only. For biomarkers from DeNovo Tumor Biopsy, this is screening and end of treatment. Appropriate summary statistics at each timepoint and ratio to screening (for continuous markers) will be provided separately for each dose escalation cohort, the dose expansion cohort, and dose expansion cohort plus the same dose escalation cohort. For continuous biomarkers, ratio to screening within each cohort will be tested using the Wilcoxon Signed-Rank Test when  $n \geq 5$  for a specific timepoint. P-values will be compared to unadjusted and adjusted alpha; alpha will be adjusted using the Bonferroni adjustment (eg,  $0.05/\#$  tests). The adjustment will be determined before data base lock.

To assess whether biomarkers are related to outcome, screening (and ratio to screening for follow-up timepoints, if available) will be summarized versus OR status (0: no OR; 1: OR). For continuous variables, the value of the biomarker will also be displayed in a box plot vs OR status (0: no OR; 1: OR), for each visit.

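### Biomarker signed-rank tests start at n = 5, where an exact two-sided p-value cannot fall below 0.0625; the minimum n and the Bonferroni divisor should be set together

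*SAP*

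**What the plan says.** SAP 6.2.5 (Biomarker endpoints) covers both the test and the criterion. For continuous markers the "ratio to screening within each cohort will be tested using the Wilcoxon Signed-Rank Test when" at least five patients have data at the timepoint. Then "P-values will be compared to unadjusted and adjusted alpha; alpha will be adjusted using the Bonferroni adjustment", with 0.05 over the number of tests as the example. On the divisor it adds only that "The adjustment will be determined before data base lock".

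Summaries are "provided separately for each dose escalation cohort, the dose expansion cohort, and dose expansion cohort plus the same dose escalation cohort", and the test is run within each cohort. The timepoints for soluble markers are also listed: "For soluble proteins this is screening, Lead-in PK D1, C1D1, C2D1, C3D1, C4D1, C6D1, EOT and follow-up at day 30". Tissue from de novo biopsy has one post-screening timepoint, end of treatment.

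On cohort size, SAP 5.1.2 describes a dose-finding design that "maximizes the number of evaluable patients treated at each dose level at 6". SAP 6 records that dose finding is complete and that only DL1, with and without lead-in, is studied. SAP 5.1.1 allows up to 8 further lead-in patients and about 40 in expansion. It also says that the study plans no formal hypothesis testing.

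**The concern.** The signed-rank statistic takes few distinct values when n is small, so its p-value has a floor set by n alone. A rule that starts testing below the n at which the criterion can be met prints p-values that could not have been significant whatever the data showed. A reader who sees p = 0.06 from five patients who all moved the same way may take it as no change.

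There is a second, conditional effect. If such tests are counted in the Bonferroni divisor, they tighten the level for the expansion and pooled cohorts, where the tests can be informative. Small cells need not be confined to escalation. The end-of-treatment biopsy is taken unless clinically contraindicated (Protocol 6.1.1), so paired tissue data may be sparse in any cohort.

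**Working it through.** The plan gives no power, sample size or attainable p-value for this test, so there is no figure of its own to reproduce.

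**Inputs**
- Testing threshold n >= 5; alpha 0.05 and 0.05/m: SAP 6.2.5. The number of tests m is not given.
- Sidedness and exact versus approximate p-value: not stated. Two-sided is assumed because the SAP's intervals are two-sided, for example the "2-sided 95% CI using the Clopper-Pearson method" for response rate. Exact is also an assumption.
- Escalation biomarker n: about 6 is assumed, from the cap in SAP 5.1.2; range discussed below.
- Post-screening timepoints for a soluble marker: 8 with lead-in, 7 in expansion, because the expansion Schedule of Activities has no lead-in visit.

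**Step 1: floor.** With no ties or zeros, the most extreme outcome is all n changes in one direction, with probability 1/2^n. The two-sided floor is 2/2^n. It lies at or below 0.05/m when n >= log2(40m).

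| n | Smallest two-sided p | Largest m for which 0.05/m is reachable |
|---|---|---|
| 5 | 0.0625 | none, not even m = 1 |
| 6 | 0.03125 | 1 |
| 7 | 0.0156 | 3 |
| 8 | 0.0078 | 6 |
| 9 | 0.0039 | 12 |
| 10 | 0.00195 | 25 |
| 14 | 0.00012 | 409 |

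Enumerating the sign patterns gives the same floors for n up to 12.

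**Step 2: other readings of the test.**
- One-sided exact: n = 5 gives 0.03125 and n = 6 gives 0.0156. So n = 5 can meet 0.05, and n = 6 can meet 0.05/2 and 0.05/3 but not 0.05/4 = 0.0125.
- Two-sided normal approximation: n = 5 gives 0.043 (0.059 with continuity correction); n = 6 gives 0.028 (0.036), above 0.05/2 = 0.025 either way.
- With 7 or 8 tests, the level is 0.05/7 = 0.0071 or 0.05/8 = 0.00625. Six patients cannot reach it under any of these variants.

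**Step 3: n needed under plausible divisors (exact, two-sided).**
- One tissue marker, three cohort sets, m = 3: log2(120) = 6.9, so n >= 7.
- One soluble marker in one cohort, m = 8: log2(320) = 8.3, so n >= 9.
- One soluble marker, all sets, m = 8 + 7 + 8 = 23: log2(920) = 9.8, so n >= 10.

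**Step 4: effect on the divisor, one soluble marker.**
- All 23 tests counted: 0.05/23 = 0.0022.
- Without the 8 escalation tests: 0.05/15 = 0.0033.

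**Step 5: what that costs at n = 40.** Approximate power is Φ(d·√(40 × 0.955) − z), where z is the two-sided critical value, d is the standardised paired change (assumed) and 0.955 is the efficiency of the signed-rank test under normality. Going from 15 to 23 tests, power falls from 56% to 51% at d = 0.5, and from 78% to 74% at d = 0.6.

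**The case against.** A reader might infer that the escalation cohort can never meet any adjusted level. The documents do not support that. The cap of 6 is on evaluable patients for dose finding. The set for sequential biomarkers (SAP 4.3.3) comes from the safety set and requires only a screening and an on-treatment value, so replaced patients may count. Up to 8 added lead-in patients follow the dose-finding assessments, and the SAP does not say which biomarker cohort they join. At 6 + 8 = 14 the floor is 0.00012, low enough for up to 409 tests. Missing samples could equally take n below 6.

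A reader might also infer that tests at n = 6 are impossible. They are not, since the SAP keeps the unadjusted 0.05 and 0.03125 meets it. Nor do the documents say that alpha is diluted: the divisor is open until before database lock and may yet leave these tests out. One-sided or uncorrected approximate p-values would also let n = 5 pass 0.05.

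It is fair, too, that the SAP gives summary statistics and ratios beside the p-values, so the p-value is not the only evidence shown. All of this stands and limits the size of the point. It does not reconcile a threshold of 5 with the criterion in the same paragraph under the usual exact two-sided test, and much of it depends on details that the SAP leaves unstated.

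**Conclusion.** The threshold does not fit its criterion. Under exact two-sided testing, which is assumed, n >= 5 is one patient too low for 0.05 and is tied to no Bonferroni level. If the escalation biomarker n is about 6, its tests cannot meet an adjusted level with two or more tests. Counting them would move the level for one soluble marker from 0.0033 to 0.0022, a loss of about 4 to 5 points of power at the assumed effects.

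The consequence is limited. These are secondary or exploratory biomarker comparisons in a study without formal hypothesis testing. No dose decision, primary endpoint or efficacy estimate depends on them, and the floor does not affect tests with n near 40.

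**What to change.** Amend SAP 6.2.5 as follows:
- State that p-values are exact and two-sided, and which biomarker cohort any added lead-in patients belong to.
- Raise the testing threshold from n >= 5 to n >= 6 for the unadjusted comparison. Show cells with n <= 5 descriptively only.
- When the divisor is set before database lock, use Tarone's rule: take the smallest K for which the number of tests with 2/2^n <= 0.05/K is at most K, and test at 0.05/K. Use the number of paired values available, not the outcomes. K is found by counting up from 1, so the rule is not circular.
- Mark cells that cannot reach the adjusted level, so that non-significance there is not read as no change. Their p-values can still be compared with 0.05.

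In the one-marker illustration, the pooled Lead-in Day 1 cell holds only lead-in patients and so also has n = 6. The rule then counts 7 expansion and 7 pooled tests, giving K = 14 and 0.05/14 = 0.0036.

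The cost is a few sentences and slightly more work to set the divisor. No new data are needed, and a few p-values that could not have been significant are no longer printed.

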### **6.2.6. Immunogenicity Endpoints**

All analyses described below are performed for all treatment groups combined.

Blood samples for avelumab immunogenicity testing will be collected pre-dose on Cycle 1, 2, 3, 4, 6 and 8. Subsequently, testing should be performed approximately every 12 weeks. All samples should be drawn within 2 hours before start of avelumab infusion. Additional samples for anti-avelumab antibodies (and simultaneous PK draws for measurement of avelumab) will be collected at the Day 30 Follow-up visit after the end of avelumab treatment.

Samples positive for ADA will be analyzed for titer and may be analyzed for nAb. As of the finalization of this SAP, the nAb assay is not yet available, therefore the analyses of nAb data described in the following sections will only be conducted contingent upon assay and data availability at the time of reporting.

Patients will be characterized into different ADA categories based on the criteria defined in [Table 7](#).

**Table 7 Patients Characterized Based on Anti-Drug Antibody Results (ADA Status)**

Category	Definition	Subjects at Risk (Denominator for Incidence)
ADA never-positive	No positive ADA results at any time point; ADA-negative patients (titer < cutpoint)	Number of patients with at least one valid ADA result at any time point
ADA ever-positive	At least one positive ADA result at any time point; ADA-positive patients (titer ≥ cutpoint)	Number of patients with at least one valid ADA result at any time point
Baseline ADA positive	A positive ADA result at baseline	Number of patients with valid baseline ADA result
Treatment-boosted ADA	A positive ADA result at baseline and the titer ≥ 8×baseline titer at least once after treatment with avelumab	Number of patients with valid baseline ADA results and at least one valid post-baseline ADA result
Treatment-induced ADA	Patient is ADA-negative at baseline and has at least one positive post-baseline ADA result; or if patient does not have a baseline sample, the patient has at least one positive past-baseline ADA result	Number of patients with at least one valid post-baseline ADA result and without positive baseline ADA result (including missing, NR)
Transient ADA response	If patients with treatment-induced ADA have (a single positive ADA result or duration between first and last positive result <16 weeks) and ADA result at the last assessment is not positive.	Number of patients with at least one valid post-baseline ADA result and without positive baseline ADA result (including missing, NR)
Persistent ADA response	If patients with treatment-induced ADA have duration between first and last positive ADA result ≥16 weeks or a positive ADA result at the last assessment	Number of patients with at least one valid post-baseline ADA result and without positive baseline ADA result (including missing, NR)

ADA: anti-drug antibody, NR = not reportable.

Patients will be characterized into different nAb categories based on the criteria in [Table 8](#). For nAb, treatment-boosted is not applicable since no titer result is available.

**Table 8 Patients Characterized Based on Neutralizing Antibody Results (nAb Status)**

Category	Definition	Subjects at Risk (Denominator for Incidence)
nAb never-positive	No positive nAb results at any time point	Number of patients with at least one valid ADA result at any time point
nAb ever-positive	At least one positive nAb result at any time point	Number of patients with at least one valid ADA result at any time point
Baseline nAb positive	A positive nAb result at baseline	Number of patients with valid baseline ADA result
Treatment-induced nAb	Patient is not nAb positive at baseline and has at least one positive post-baseline nAb result; or if patient does not have a baseline sample, the patient has at least one positive post-baseline ADA result	Number of patients with at least one valid post-baseline ADA result and without positive baseline nAb result (including missing, NR)
Transient nAb response	If patients with treatment-induced nAb have (a single positive nAb result or duration between first and last positive result <16 weeks) and nAb result at the last assessment is not positive.	Number of patients with at least one ADA valid post-baseline result and without positive baseline nAb result (including missing, NR)
Persistent nAb response	If patients with treatment-induced nAb have duration between first and last positive nAb result ≥16 weeks or a positive nAb result at the last assessment	Number of patients with at least one valid post-baseline ADA result and without positive baseline nAb result (including missing, NR)

ADA = antidrug antibody, nAb = neutralizing antibody, NR = no result.

The number and percentage of patients in each ADA and nAb category will be summarized.

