7.3. Immunogenicity Assessment

A total of 3.5 mL of whole blood will be collected into a SST at the designated times to provide serum for evaluation of avelumab immunogenicity. Immunogenicity blood samples will be assayed for anti-avelumab antibodies using a validated analytical method. All of the samples that are positive for ADA may also undergo characterization for neutralizing antibodies. Additional details regarding the collection, processing, storage, and shipping of the blood samples will be provided in the Study Manual.

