### **5.2.3. Presentation of continuous and qualitative variables**

Continuous variables will be summarized using descriptive statistics ie, number of non-missing values and number of missing values [ie, n (missing)], mean, median, standard deviation (SD), minimum, maximum and first and third quartile (Q1 and Q3).

Qualitative variables will be summarized by frequency counts and percentages. Unless otherwise specified, the calculation of proportions will include the missing category. Therefore counts of missing observations will be included in the denominator and presented as a separate category.

In case the analysis refers only to certain visits, percentages will be based on the number of patients still present in the study at that visit, unless otherwise specified.

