## nAb

- nAb ever-positive versus nAb never-positive
- nAb: treatment-induced nAb versus nAb never-positive or baseline nAb positive

Data listings will include immunogenicity data together with relevant PK, safety and efficacy data.

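### SAP Table 8 counts an ADA-positive patient with no valid nAb result as nAb never-positive, so nAb incidence would be understated if only some ADA-positive patients are tested

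*SAP*

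**What the plan says.** Table 8 in SAP section 6.2.6 assigns a patient to nAb never-positive on one condition: "No positive nAb results at any time point". The never-positive and ever-positive rows share a denominator based on the other assay: "Number of patients with at least one valid ADA result at any time point". No row requires a valid negative nAb result, and there is no row for untested or unevaluable patients. Three rows do keep patients whose baseline nAb result is missing, so absent results were foreseen at baseline.

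Testing is optional. SAP 6.2.6 states: "Samples positive for ADA will be analyzed for titer and may be analyzed for nAb". Protocol 7.3 agrees: "All of the samples that are positive for ADA may also undergo characterization for neutralizing antibodies". The SAP adds that the nAb assay did not exist when it was finalized, and that the nAb analyses are "contingent upon assay and data availability at the time of reporting".

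SAP 6.2.6.3 uses the status to form two contrasts for PK, safety and efficacy: "nAb ever-positive versus nAb never-positive", and "treatment-induced nAb versus nAb never-positive or baseline nAb positive".

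The general rule in SAP 5.2.3, which applies unless something else is specified, is that "counts of missing observations will be included in the denominator and presented as a separate category".

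**The concern.** An ADA-negative patient may fairly be treated as nAb-negative, because only ADA-positive samples go forward for nAb testing. The difficulty is confined to the ADA-positive patient whose samples were not tested or gave no valid nAb result. That patient's nAb status is unknown, yet the patient meets the never-positive definition and stays in the denominator. A reader of the table could not tell a patient who tested negative from one who was never tested.

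Neutralizing antibodies belong to a listed secondary endpoint (Protocol 2.2), and Protocol 9.5.1.3 commits to reporting the percentage of patients positive for them. Missing results would lower that percentage. They would also place some possible positives in the reference group of the 6.2.6.3 contrasts.

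**Working it through.** The plan states no expected nAb incidence, so there is no figure to reproduce. The check applies Table 8 to one type of patient and then sizes the effect under stated assumptions.

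**Classification.** Take a patient who is ADA-positive after baseline and has no nAb result.
- The plan allows this, because testing is optional in both documents.
- The patient has no positive nAb result, so the never-positive condition is met.
- The patient has a valid ADA result, so the patient is in the denominator.
- The patient therefore enters the reference group of the first 6.2.6.3 contrast.

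**Inputs.** N = 55 patients with a valid ADA result, taken from the approximate maximum enrolment in SAP 5.1.1. The rest are assumptions, since the documents are silent:
- A, the number ADA-positive: 4 to 12.
- q, the truly nAb-positive share of A: 25% to 75%.
- t, the tested share of A: 25% to 100%, with testing unrelated to true nAb status.

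**Formulas.**
- True incidence = A·q/N.
- Reported incidence = A·t·q/N, so the relative shortfall is 1 − t.
- Incidence with untested ADA-positive patients removed from the denominator = A·t·q/(N − A(1 − t)).
- Truly positive share of the never-positive group = A·q·(1 − t)/(N − A·t·q). In the first contrast, a true mean difference shrinks by this fraction.

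**Central example, A = 8 and q = 50%** (true incidence 4/55 = 7.3%):

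| Tested share | Reported | Untested removed from denominator | True positives among never-positive |
|---|---|---|---|
| 100% | 4/55 = 7.3% | 4/55 = 7.3% | 0/51 = 0% |
| 75% | 3/55 = 5.5% | 3/53 = 5.7% | 1/52 = 1.9% |
| 50% | 2/55 = 3.6% | 2/51 = 3.9% | 2/53 = 3.8% |
| 25% | 1/55 = 1.8% | 1/49 = 2.0% | 3/54 = 5.6% |

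**Range.** The extreme corner is A = 12, q = 75%, t = 25%. The expected reported incidence is 2.25/55 = 4.1% against 9/55 = 16.4%, a gap of 12.3 percentage points. The never-positive group is then 6.75/52.75 = 12.8% truly positive. At t = 100% both errors are zero whatever A and q are.

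**Effect of the denominator.** Removing untested patients hardly moves the estimate (3.6% to 3.9% at half tested), because those removed are all ADA-positive while every ADA-negative patient stays. Among ADA-positive patients with a valid nAb result, the example gives 2/4 = 50%, the assumed truth. Counting the untested as negative gives 2/8 = 25%.

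**The case against.** The strongest reply is that the optional wording operates at the level of the trial. No nAb assay existed when the SAP was finalized, so the authors could not promise testing. If no assay arrives, no nAb table is produced. If one arrives and every ADA-positive sample is run, Table 8 gives the right answer. Nothing in either document plans partial testing. This stands as a limit: the error is conditional. It does not remove the point, because the availability clause settles whether the analyses are run and not how an untested patient is classed once some results exist.

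A second reply is that SAP 5.2.3 shows missing values separately. That rule gives way where something else is specified, and Table 8's definition already takes in the untested patient. The listings may reveal a testing gap, but the summary table would not.

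A reader might infer four stronger things that the documents do not support:
- That nAb incidence is understated as a matter of fact. This needs some ADA-positive patients to go untested and some of those to be truly positive; the documents establish neither.
- That every nAb row is understated. The treatment-induced row can err upward, since a patient with no baseline sample enters it on a positive post-baseline ADA result, without a positive nAb result.
- That the contrasts are seriously weakened. ADA-negative patients dominate the never-positive group, so dilution is small in most of the assumed range. The SAP plans no formal hypothesis testing, the visible nAb repeat of the PK analysis depends on the data, and part of the later text is redacted.
- That correcting the denominator cures the incidence. The working shows that it does not.

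**Conclusion.** The point holds in conditional form. As written, Table 8 classes an ADA-positive patient with no valid nAb result as never-positive, and no other rule in the plan reverses this. If only some ADA-positive patients are tested, and testing is unrelated to true nAb status, ever-positive incidence is understated in relative terms by the untested share: 25% with three quarters tested, 50% with half tested, nothing with all tested. The absolute size cannot be derived from the documents. Over the assumed ranges the shortfall runs from 0 to 12.3 percentage points, and from 7.3% to 3.6% in the central example at half tested. Contamination of the never-positive group is 3.8% in that example and at most 12.8% in the range. This affects a descriptive secondary endpoint; the primary DLT analysis is untouched.

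**What to change.** Amend Table 8 and section 6.2.6.3 of the SAP before any nAb data are reported:
- Define nAb never-positive as ADA-negative at all valid assessments, or ADA-positive with valid nAb results and none positive.
- Add a category, nAb not evaluable, for ADA-positive patients with neither a positive nor any valid nAb result. Show its count as its own row, and exclude it from both nAb contrasts in 6.2.6.3.
- State how a patient with only some ADA-positive samples tested is classed, in particular whether one valid negative result is enough. Too strict a rule would discard patients with several valid negatives.
- Alongside the all-patient percentage, report nAb positivity among ADA-positive patients with a valid nAb result, together with the number of ADA-positive patients untested. This addition is needed because a change of denominator leaves the understatement almost unchanged.

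The cost is revised table wording, one derived category, one extra row and slightly smaller comparison groups. No new data collection is needed.

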#### 6.2.6.1. Time to and Duration of ADA and nAb response

The ADA and nAb analyses described below will include patients with treatment-induced ADA or nAb, respectively.

Time (weeks) to ADA response is defined as:

$$(\text{Date of first positive ADA result} - \text{date of first dose of avelumab} + 1)/7.$$

Time to ADA response will be summarized using simple descriptive statistics (mean, SD, median, min, max, Q1, Q3).

Duration (weeks) of ADA response is defined as:

$$(\text{Date of last positive ADA result} - \text{date of first positive ADA result} + 1)/7.$$

Duration of ADA response will be censored if:

- the last ADA assessment is positive AND patient is ongoing treatment with avelumab, or

- the last ADA assessment is positive AND patient discontinued treatment with avelumab AND the last planned ADA assessment (day 30 follow-up visit) is after the cut-off date.

Time to nAb response and duration of nAb response are defined similarly based on first and last positive nAb result.

Kaplan-Meier estimates (product-limit estimates) will be presented together with a summary of associated statistics including the median ADA response time with 2-sided 95% CIs. ADA response rates at different timepoints will be estimated with corresponding 2-sided 95% CIs. The CIs for the median will be calculated according to Brookmeyer and Crowley (1982) and the CIs for the survival function estimates will be derived using the log-log transformation according to Kalbfleisch and Prentice (2011) (conftype=loglog default option in SAS Proc LIFETEST) with back transformation to a CI on the untransformed scale. The estimate of the standard error will be computed using Greenwood's formula.

Duration of ADA response will be displayed graphically and analyzed using Kaplan-Meier methodology. If the number of patients with ADA response is small, the Kaplan-Meier method may not provide reliable estimates. In this case, only descriptive statistics or listings will be provided

As data permit, the analyses described above will be repeated for patients with treatment-induced nAb.

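### SAP Table 8 counts a patient with no baseline sample as treatment-induced nAb on a positive ADA result alone, so the same patient can also be nAb never-positive

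*SAP*

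**What the plan says.** SAP Table 8 gives two routes to treatment-induced nAb. The first is "Patient is not nAb positive at baseline and has at least one positive post-baseline nAb result". The second follows directly: "or if patient does not have a baseline sample, the patient has at least one positive post-baseline ADA result".

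Table 7, which defines ADA status, has a matching second clause: "or if patient does not have a baseline sample, the patient has at least one positive past-baseline ADA result". There the category is ADA, so ADA is the right analyte.

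Other provisions bear on the point:

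- Table 8 defines nAb never-positive as "No positive nAb results at any time point".
- Section 6.2.6 says of testing: "Samples positive for ADA will be analyzed for titer and may be analyzed for nAb". It also makes all nAb analyses conditional on assay and data availability, because the assay did not exist when the SAP was finalised.
- Section 6.2.6.1 sets the population: "The ADA and nAb analyses described below will include patients with treatment-induced ADA or nAb, respectively". It then sets the variables: "Time to nAb response and duration of nAb response are defined similarly based on first and last positive nAb result".
- Section 6.2.6.3 sets one of its two nAb comparisons as "nAb: treatment-induced nAb versus nAb never-positive or baseline nAb positive".

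Nothing elsewhere in the SAP or protocol corrects the second clause of Table 8.

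**The concern.** A positive ADA result does not establish a positive nAb result: the ADA-positive sample may be nAb-negative, or may never have been tested for nAb. The second clause of Table 8 ignores this and lets ADA stand in for nAb whenever the baseline sample is missing. The categories then contradict each other for the same patient.

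Immunogenicity is a stated secondary objective, and nAb is part of its endpoint. If the clause is followed, the treatment-induced nAb count can include patients with no evidence of neutralising antibody, and the groups compared in section 6.2.6.3 are not exclusive. A programmer would have to code the contradiction or depart from the SAP without a documented reason.

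**Working it through.** The plan states no figure to reproduce. The check is a logical one, followed by a scale calculation.

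**Step 1: classify every combination.** Take four baseline states (sample missing; ADA-negative; ADA-positive and nAb-negative; ADA-positive and nAb-positive). Cross them with four post-baseline states (ADA-negative; ADA-positive and nAb-negative; ADA-positive and not tested for nAb; ADA-positive and nAb-positive). That gives 4 × 4 = 16 combinations. Apply Table 8 as written, then with nAb in place of ADA in the missing-baseline clause. The four rows with no baseline sample are:

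| Post-baseline state | Treatment-induced nAb, as written | nAb never-positive | Treatment-induced nAb, corrected |
|---|---|---|---|
| ADA-negative | no | yes | no |
| ADA-positive, nAb-negative | **yes** | **yes** | no |
| ADA-positive, nAb not tested | **yes** | **yes** | no |
| ADA-positive, nAb-positive | yes | no | yes |

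The other 12 combinations have a baseline sample, and none of them conflicts. As written, 2 of 16 combinations are in both categories. After the correction, 0 of 16 are, and the remaining 14 classifications are unchanged. The result is the same whether or not the first clause (not nAb positive at baseline) is read as already covering a patient with no baseline sample.

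**Step 2: follow the affected patient through the analyses.**

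- *Incidence.* The Table 8 denominator for treatment-induced nAb admits patients with a missing baseline, so the patient is in the denominator and wrongly in the numerator.
- *Transient or persistent.* Both rows require treatment-induced nAb plus some pattern of positive nAb results. I read the unqualified positive results in the transient row as nAb, as the persistent row states. With no positive nAb result, the patient fits neither row, so the two no longer sum to treatment-induced nAb.
- *Time to and duration of response.* The patient belongs to the section 6.2.6.1 population but has no first or last positive nAb date, so neither value can be computed.
- *Comparison by nAb status.* In section 6.2.6.3 the patient is in the treatment-induced group and also in the never-positive part of the comparator.

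**Step 3: scale.** The documents do not give the number of missing baseline samples. Assume k affected patients and a denominator of 55, the approximate total enrolment projected in SAP section 2.2; section 6.2.6 combines all treatment groups. The added incidence is 100 × k / 55:

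- k = 0: 0 points
- k = 1: 100 × 1 / 55 = 1.8 points
- k = 2: 100 × 2 / 55 = 3.6 points
- k = 3: 100 × 3 / 55 = 5.5 points

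A smaller denominator would raise these in proportion.

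**The case against.** The strongest reply is that the affected set may be empty. A pre-dose Cycle 1 sample is scheduled for every patient, and the error needs three things together: no baseline sample, a later positive ADA result, and no positive nAb result. The nAb analyses may also never be run, and the repeats for nAb in sections 6.2.6.1 and 6.2.6.3 are made only as data permit. All of this stands and limits the size of the point. It does not rescue the definition: Table 8 provides for missing baselines, so the SAP itself treats the case as possible.

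Four stronger readings are tempting, and the documents do not support them:

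- *A reader might infer that nAb-positive counts will be small, so that one misclassified patient would visibly shift the incidence.* The documents give no nAb rate and no count of missing baselines. Any shift is conditional on an assumed number.
- *A reader might infer that false values would enter the time-to and duration summaries.* They would not. Both rest on positive nAb results, so the affected patient has no value at all. The defect is a mismatch between the stated population and the patients with a computable value.
- *A reader might infer that the ADA-based denominators in Table 8 are the same mistake.* They can be deliberate, since nAb testing is foreseen only for ADA-positive samples.
- *A reader might take it as fact that the clause was copied from Table 7.* The parallel wording makes that likely, but the documents do not say so.

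It can also be said that the corrected clause is largely redundant, because a patient with no baseline sample can already satisfy the first clause read literally. That is fair, and it does no harm.

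**Conclusion.** The point holds: Table 8 is wrong as written. It classifies a patient with no baseline sample as treatment-induced nAb on a positive ADA result alone. If that patient's ADA-positive samples are nAb-negative or untested, the patient is nAb never-positive as well. Patients with a baseline sample are classified correctly.

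The practical effect is probably small. It is zero if the nAb analyses are not run or no baseline sample is missing. On the assumption of 1 to 3 affected patients in a denominator of about 55, it adds 1.8 to 5.5 percentage points to treatment-induced nAb incidence. The affected output is descriptive and concerns a secondary endpoint; DLT assessment and selection of the MTD or RP2D do not use it.

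**What to change.** In the treatment-induced nAb row of SAP Table 8, replace ADA with nAb in the missing-baseline clause, so that a patient without a baseline sample needs at least one positive nAb result after baseline. Keep the ADA-based denominators. This removes both conflicting combinations and changes no other classification.

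The cost is one word in the SAP. No new data are needed, and no protocol amendment, since protocol section 9 requires one only for major changes to the primary endpoint or its analysis. The change is best made before any nAb results are available.
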